4.5 Sample size

Our sample size will be determined by the size of the community who engages with the research. Based on an estimated Mongolian community of 1300 people living in London, we estimate 70% of these to be adults aged 18+ (n=910), and of these we will aim to recruit and engage 500-600 people. We will use local networks and social media (e.g. well-established facebook groups) to try to reach as many of the community of individuals aged 18+ with information and an invitation to participate. We will run up to a maximum of five screening events, screening approximately 100 per day to allow screening of 500-600 individuals.

Approximate estimated numbers per recruitment group based on published prevalence estimates with an expected screening number of ~500 (**figure 4**):

- People living with HBV (~7.5%) (19-22, 41, 42) (n= ~38)
- ~35% living with HBV/HDV coinfection (43) (n=~13)
- People living with HCV (~6%) (n=~30) (39)
- People living with MASLD (~30%) (44) (n=~150)

This will be a small study with limited statistical power. However, our primary objective is to establish the prevalence of hepatitis B and C virus infection in this study.

Using the formula for calculating sample size for prevalence studies $n = Z^2P(1-P)/d^2$, where:

- n: is the sample size
- Z: is the statistic for the confidence level (1.96 i.e. 95% confidence interval)
- P: is the expected prevalence (7.5%)
- d: is the precision (0.05, +/- 2.5%)

Using the above estimated parameters, a sample size of approximately 427 is needed to determine a prevalence of HBV of 7.5%.

Other analyses will be exploratory, investigating trends using correlation with lipidomic, transcriptomic and sequencing data which can be further analysed with a more targeted approach.

Given the low prevalence of HIV in Mongolia (~0.1%), we do not expect to pick up any new diagnoses in this screening programme. There are also low rates of HBV/HCV coinfection (0.4%), therefore it is unlikely we will pick up new diagnoses in this cohort (45). However, we will also recruit people living with HIV or other co-infections if we identify them and they are willing to participate in the research project.

[figure not shown]

Figure 4: Schematic illustrating expected numbers in analysis groups based on published prevalence and a sample size of 500. N.B. we will only collect blood samples from up to 50 participants with no MASLD and no BBV (i.e. “healthy controls”). Abbreviations: MASLD - metabolic dysfunction-associated steatotic liver disease; BBV - blood borne virus; HBV - hepatitis B virus; HCV - hepatitis C virus; Other combinations include HBV+HCV, and human immunodeficiency virus (HIV) monoinfection or coinfections.

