HDV is a coinfection that can be established only in the setting of HBV infection and causes accelerated liver disease. To date, HDV treatment options have been limited, but a new treatment is recently available (Myrcludex, Gilead), and there is a focus from public health agencies, clinicians and pharmaceutical companies on identifying and treating those with HDV infection (10, 11).

(iv) HIV & Syphilis

No disease exists in a silo. Routes of transmission for HIV and syphilis overlap with hepatitis B, C and D (sexual, mother-to-child, and blood). The World Health Organisation introduced the "triple elimination" agenda in 2023, to build cross programme efficiencies to strengthen and leverage elimination of HIV, syphilis and HBV, particularly in the context of mother-to-child transmission (12). Since we have access to a multiplexed HIV/syphilis point-of-care-test (POCT), we are a team skilled in screening and treating these conditions and effective

treatments exist for both HIV and syphilis, we will screen for these infections in the MOLO study.

Metabolic dysfunction associated steatotic-liver disease

Metabolic dysfunction-associated steatotic liver disease (MASLD) is defined as steatosis (fat in the liver) occurring with at least one criterion for metabolic syndrome (hypertension, diabetes, dyslipidaemia, obesity) (**figure 2**). In 2023, this nomenclature replaced non-alcoholic fatty liver disease (NAFLD), with the aim to reduce stigma and more accurately reflect the disease pathogenesis (13). MASLD is a global health problem affecting 1.7 billion people worldwide and, like viral hepatitis, can lead to cirrhosis and liver cancer (14). However, the interplay between MASLD and viral hepatitis, in particular HBV, is not well understood (15). The intersection between viral hepatitis and MASLD is therefore an area of expanding interest for risk stratification, particularly in the context of a global increase in the prevalence of both metabolic syndrome and MASLD (16, 17).

[figure not shown]

Figure 2: Schematic illustrating metabolic dysfunction-associated steatotic liver disease (13). Abbreviations: CAP - controlled attenuation parameter; BMI - body mass index; HbA1c - glycosylated haemoglobin; HDL - high density lipoprotein. CAP ≥ 230 (18).

Focus on the Mongolian Community

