3.1 Primary Objectives

There are three domains to this study design contributing to the primary objectives (**figure 1**).

Clinical screening domain (part 1):

Among the London Mongolian community:

- Estimate the prevalence the number of people living with chronic viral hepatitis (HBV, HCV and HDV).
- Estimate the prevalence MASLD and presence of metabolic risk factors (obesity, hypertension, diabetes and dyslipidaemia).
- Develop community engagement and develop a stakeholder group to support the establishment of a screening and research programme for chronic viral hepatitis infection (HBV, HCV, HDV).
- To raise awareness of liver health, in particular chronic viral hepatitis (HBV, HCV and HDV) and metabolic dysfunction-associated steatotic liver disease (MASLD)

Laboratory research domain (laboratory test, part 2):

Among the London Mongolian community:

- Compare lipidomic profiles between PLWHB and MASLD, PLWHB only, people living with MASLD only and people without CHB or MASLD to investigate the interplay between the two major global causes of liver disease.
- Identify demographic, clinical and laboratory factors (e.g. viral sequencing, host immune and lipidomic profile, host HLA sequencing) associated with liver disease among people living with chronic viral hepatitis.

Qualitative domain (part 3):

Among the London Mongolian community:

- To understand attitudes, facilitators and barriers to testing and accessing healthcare for chronic viral hepatitis.

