- For those who test positive for HIV, HBV, HCV or HDV we will contact their specialist care provider before the end of the study (~12 months post diagnosis) to ascertain clinic attendance, which will allow us to understand linkage and retention in specialist care.
- Anonymised data will be assimilated and shared (including in publication format) to support service development.
- We will retain anonymised data and samples long term such that material can be reused for future analyses relevant to chronic BBV infection and liver disease, subject to terms of consent and ethical permission (those who have consented for research).

Approach for all participants, after providing information:

1. Baseline data collection -
 - NHS identifiers: NHS number, name, date of birth - information to remain in clinical domain only.
 - Questionnaire (demographics, viral hepatitis and metabolic risk factors)
2. Point of care testing (POCT)* for HIV, HBV, HCV, syphilis.
3. Measurement of biometric data (weight, height, waist circumference).
4. For all those who are POCT positive, and a subset of at least 100 who are POCT negative (more if capacity allows), we will offer fibroscan assessment (non-invasive point of care test to assess liver health):
 - Transient elastography (TE) - assessment of inflammation / fibrosis
 - Controlled attenuation parameter (CAP) - assessment of steatosis
5. Venous bloods (see **table 1**)**
 - All participants:
 - Since Mongolians may be a high risk category for diabetes, (31) everyone will be offered a glycosylated haemoglobin blood test (HbA1c, in line with the NHS optimising tests in primary care document (32)). We will not test anyone with a pre-existing diagnosis of diabetes.
 - Lipid profile will be offered for those aged >40 years, BMI >23 or they have a family history of high cholesterol or heart disease (33). We will not test people already taking lipid lowering medication.
 - HBV serology for surface and core antibody, to establish if susceptible to HBV infection.
 - If HBV positive POCT: Hepatitis B surface antigen (HBsAg), HBV viral load, HBV core antibody, HBV e Antibody/Antigen, hepatitis D antibody, liver function tests.
 - If HCV positive POCT: HCV antibody, HCV RNA, liver function tests.
 - HIV positive on POCT: HIV antibody/antigen, HIV viral load.

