A WHO assessment of the OraQuick anti-HCV test (OraSure Technologies, Pennsylvania, USA) revealed sensitivity 100% (97.8% to 100.0%) and specificity 99.4% (97.3% to 99.8%) (38). Age-adjusted chronic infection prevalence is estimated to be 6% , therefore this test should not give rise to any false negatives and 3 false positive results (39).

(ii) Laboratory research domain (part 2):

7. For all those who are POCT positive, and up to ~ 100 who are POCT negative, we will offer the opportunity to enrol in research, which includes:
- o 3 additional blood tubes for research (pathogen sequencing, metabolomics, biomarkers, immune profile, host genetic sequencing).
 - All those with chronic viral hepatitis infection who consent for research will have these additional bloods.
 - For those without BBV infection, we will only collect additional bloods on:
 - o Maximum 50 of those without steatosis
 - o Maximum 50 of those with steatosis

(iii) Qualitative domain (part 3)

During the screening event, participants will be asked to indicate whether they consent to future contact to be invited into a qualitative study. We will use methods similar to those previously published, in a study which investigated barriers and opportunities to HBV testing in a UK Somali population (40). Our team brings expertise in community engagement and qualitative data collection in both primary ([name]) and secondary ([name]) care settings and working with international communities ([name]).

There will be 2-4 focus groups of 5-8 participants (number of groups will be limited by idea saturation, willing participants, time and cost). We will use purposive sampling to identify a range of community members of different ages, time in the UK, gender etc., who are likely to have a variety of views on chronic viral hepatitis testing and access to healthcare. To avoid the risk of accidental disclosure of infection status, we will only invite participants who are not living with a blood borne virus.

We will perform a semi-structured 1:1 interview of a sample (~5) people with chronic viral hepatitis to explore barriers and facilitators to diagnosis, linkage-to and retention-in-care, stigma and discrimination, and other topics relevant to chronic viral hepatitis diagnosis and management.

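### Section 4.5 counts MASLD over all ~500 screened, but the committed Fibroscan coverage would identify only about 39–50 cases, and no rule says which POCT-negatives are scanned

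*Protocol*

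**What the plan says.** MASLD prevalence is part of the primary aim in section 3 and is listed among the primary objectives in section 3.1: "Estimate the prevalence MASLD and presence of metabolic risk factors (obesity, hypertension, diabetes and dyslipidaemia").

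Section 4.5 gives approximate numbers per recruitment group "with an expected screening number of ~500". For MASLD the entry is "People living with MASLD (~30%) (44) (n=~150"). Figure 4 shows the analysis groups on the same base of 500.

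Section 2 says that MASLD "is defined as steatosis (fat in the liver) occurring with at least one criterion for metabolic syndrome". The study's measure of steatosis is part of the Fibroscan assessment in section 4.3(i) step 4: "Controlled attenuation parameter (CAP) - assessment of steatosis". The same step says who gets it: "For all those who are POCT positive, and a subset of at least 100 who are POCT negative (more if capacity allows), we will offer" the scan. Section 5 lists Fibroscan as one of five data-collection steps without restriction, but refers back to section 4.3 for detail. Scanning capacity is not stated anywhere.

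Section 4.3(ii) limits research bloods in people without BBV infection, including "Maximum 50 of those with steatosis" and the same number without. Section 9 item 1 lists MASLD among the prevalences to be described and promises suitable weighting with 95% confidence intervals. It does not say what the weights are based on.

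**The concern.** The figure in section 4.5 and the procedure in section 4.3 use different denominators. Someone who has not had CAP cannot be classed as having or not having MASLD, so a count taken over everyone screened describes people whom the committed procedure will not classify. A reader of section 4.5 would expect about 150 identified cases for a primary objective and for the group comparisons in section 9.

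The second issue is who is scanned. POCT-positives are all offered a scan, and section 4.3 step 6 allows results to be picked up later in clinic. POCT-negatives are a subset whose size depends on capacity and whose selection is not described. Staff could scan whoever is free, or whoever looks at metabolic risk, and nothing in the protocol would reveal it. The negatives carry most of the weight in any estimate for the screened population, so the MASLD prevalence depends on how they were chosen. That choice is made at no more than five events and cannot be reconstructed later.

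**Working it through.** **Inputs**
- Screened: ~500 (section 4.5).
- MASLD prevalence: 30% (section 4.5).
- BBV-positives: 38 HBV + 30 HCV = 68 (section 4.5), or 30–40 (Study Summary). The two sources differ, so both are carried as a range. The 0.4% HBV/HCV coinfection rate in section 4.5 would remove about 2 people.
- Fibroscan: all POCT-positives plus at least 100 POCT-negatives (section 4.3 step 4).

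**The plan's own figure.** 0.30 × 500 = 150. It reproduces, with everyone screened as the denominator.

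**Cases at the committed minimum**
- With 30 positives: 30 + 100 = 130 scanned (26% of 500); 0.30 × 130 = 39.
- With 40 positives: 140 scanned (28%); 0.30 × 140 = 42.
- With 68 positives: 168 scanned (33.6%); 0.30 × 168 = 50.4.

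Finding 150 among 168 would need a prevalence of 150/168 = 89%.

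**Precision.** With all 500 scanned: 1.96 × √(0.30 × 0.70/500) = 4.0 points. For a two-stratum estimate weighted to those screened, the half-width is 1.96 × √(W₊² × 0.21/n₊ + W₋² × 0.21/n₋), where W is each stratum's share of the 500.
- 68 positives, 100 negatives: W₊ = 0.136, W₋ = 0.864; half-width 7.9 points.
- 30 positives, 100 negatives: W₊ = 0.06, W₋ = 0.94; half-width 1.96 × √(0.0000252 + 0.0018556) = 8.5 points.

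No finite-population correction is used, as in the plan's own HBV formula.

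**More than the minimum** (68 positives, 30% in both strata)

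| POCT-negatives scanned | Total scanned | MASLD identified | Weighted half-width |
|---|---|---|---|
| 100 | 168 | ~50 | ±7.9 |
| 200 | 268 | ~80 | ±5.7 |
| 300 | 368 | ~110 | ±4.7 |
| 432 (all) | 500 | ~150 | ±4.0 |

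**Composition at the minimum.** BBV-positives are 30/130 = 23% to 68/168 = 40% of those scanned, against 30/500 = 6% to 68/500 = 13.6% of those screened. Once weighted back, the POCT-negatives carry 86–94% of the estimate.

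**The case against.** The strongest reply is that the minimum is not a maximum. Section 4.3 says at least 100 and allows more where capacity permits. A reader might infer that 150 cases cannot be found or that only a third will ever be scanned. The protocol does not support that: if nearly everyone is scanned, 150 is attainable. What stands is that it makes no commitment beyond the minimum, and even 300 negatives would give about 110.

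The ~150 is also an approximate expectation from published prevalence, not a recruitment target. Section 4.5 admits limited power, calculates precision only for HBV, describes HBV and HCV prevalence as its primary objective and calls other analyses exploratory. That is fair, and no MASLD precision has been promised and missed. But sections 3 and 3.1 still make MASLD prevalence primary.

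A reader might also infer that an unweighted proportion will be reported, and so a biased one. Section 9 promises weighting, and the exact weights may properly sit in an analysis plan. Any unweighted bias could also go either way. If MASLD were 30% in negatives (an assumption), it would be −4.0 points with 15% in positives, zero with 30% and +5.4 with 50%. Weighting by POCT status removes this imbalance. It does not repair unknown selection within the negatives.

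Two further readings fail. The ceiling of 50 with steatosis is a maximum, so falling short of it is no defect. It can also be reached: at 30%, 50/0.30 = 167 negative scans would suffice, which section 4.3 permits, and steatosis is at least as common as MASLD. Nor does the 50/50 limit on research bloods show that scanning will be steered towards steatosis. It governs bloods, and steatosis is known only after the scan.

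**Conclusion.** The point holds as a mismatch between sections 4.5 and 4.3, together with a missing selection rule. At the committed Fibroscan minimum, about 39–50 MASLD cases are identifiable rather than ~150, with a 95% half-width of about ±8 points rather than the ±4.0 that scanning all 500 would give. The shortfall narrows as more negatives are scanned and disappears only at near-complete coverage.

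This assumes 30% MASLD in both strata, full uptake of the offered scan, and POCT-positives counted as the expected HBV and HCV infections. Lower uptake would reduce the yield. Positive HIV or syphilis tests, or false positives, would add a few scans.

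No direction or size of bias in the prevalence estimate can be established from the protocol. What can be said is that representativeness of the POCT-negatives, on whom most of the estimate rests, is left to chance on the day and cannot be restored by later weighting. The selection rule therefore has to be in place before the screening events.

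**What to change.** 1. **Section 4.5.** Say that ~150 is the number expected to have MASLD among those screened. Add the number identifiable at the Fibroscan minimum (about 40–50) and its precision (about ±8 points), with the figures for larger scan numbers.
2. **Section 4.3 step 4.** Choose POCT-negatives for Fibroscan by a systematic rule set before each event. One example is every k-th POCT-negative in registration order, with k set from that day's scanning capacity so that spare capacity is still used. The rule should not depend on BMI, metabolic risk or the research-blood ceilings. Record k and the number of POCT-negatives at each event, so that selection probabilities are known. Scans done outside the rule need not be refused, but should be flagged and left out of the prevalence estimate.
3. **Section 9 item 1.** Name POCT stratum as a basis of the MASLD prevalence weights.

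The cost is protocol wording, a simple list rule on the day and one extra recorded field. No additional participants or scans are needed. The drawback is a less favourable stated count and precision for MASLD.

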5 STUDY SCHEDULE

Enrolment process

To support the development of this protocol, we have reached out via the Mongolian Community Organisation (based in West London) to seek feedback around the concept and approaches to be taken by the study, using a SurveyMonkey questionnaire in Mongolian. We will continue to partner with this organisation throughout the project so that we are responsive to the community’s needs and feedback.

In advance of our clinical screening events, meetings will be convened with members of the Mongolian community to engage with them in planning the specific details of outreach and screening activities, including details of communication strategies, community awareness, approaches to connecting and provision of culturally sensitive and accessible information.

Prior to screening events, potential participants will be contacted with written information (in Mongolian and/or in English) and study details alongside an invitation to attend a screening event. The study will be advertised via a Mongolian community facebook group and word of mouth and posters via the Mongolian Community Organisation. Participants will be asked to register interest in a secure google form, and the patient information sheet will be emailed or handed out in person in advance of the day. They will also be provided with a point of contact for further information about the project. We will allow enrolment of participants who have not pre-registered, since there will be

an information session ahead of the practical screening process. If the person is interested but needs more time to consider, we will give them details of the next screening event to attend.

Study enrolment will take place during the screening event, facilitated by a trained member of the clinical research team, alongside a Mongolian interpreter if required. Potential participants will be provided with written and verbal information, can ask questions, and confirm their participation in clinical screening verbally (as per standard of care for clinical procedures), and research participation with written informed consent.

Screening

Participants will be screened for eligibility, being able to take part if they are aged 18 years or older on the screening date and being able to provide valid informed consent. There are no other inclusion/exclusion criteria.

Data collection

Data will be collected through the following five-step pathway (for more detail of specific tests see section 4.3)

- Questionnaire (see appendix) - demographic, metabolic and viral hepatitis risk factors, comorbidities
- Biometric data: weight, height, waist circumference
- Point of care tests (fingerprick testing)
- Venous blood samples (see Table 1)
- Fibroscan (TE and CAP score)

Follow up

As previously mentioned in section 4.3, we will contact the referral clinic to ascertain information about appointment attendance up to one year post diagnosis to ascertain retention-in-care. We will arrange appropriate clinical follow up for conditions diagnosed during the outreach event:

1. Chronic viral hepatitis
 - Participants found to have a new diagnosis of viral hepatitis (HBV/HDV/HCV) or HIV or syphilis, or those who are known but not under follow up, will be referred to specialist care.
 - Our specialist viral hepatitis clinics at Mortimer Market Centre and University College London Hospital will lead in providing clinical follow-up and will provide a default appointment for individuals who need review based on the results of BBV screening. For any participants who wish to be referred to an alternative secondary/tertiary care provider, this can be arranged as per routine protocols for referrals between NHS centres. Our existing clinical team includes a peer support worker and members of the Find-and-Treat service who can provide additional support and information, including accompanying people to clinic visits if needed.

2. Hypertension
 - Participants will be informed of their blood pressure results on the day. This information will be entered into a paper form for them to take away, and will be provided alongside basic lifestyle advice.
 - We will follow NICE guidelines on hypertension diagnosis and management:
 - If >140/90, repeat blood pressure and take the lowest of 2 recordings. Suggest attendance for referral for ambulatory BP monitoring/ optimising current hypertension medications if already diagnosed with hypertension.
 - If >180/120, the blood pressure will be repeated. If it remains >120/180 for 3 readings, then they will be advised to attend Accident & Emergency for further assessment.
3. Raised BMI
 - Participants will be informed of their BMI and given their results along with information on lifestyle advice to take away.
 - A letter will be sent to the GP to inform them of the results.
4. Raised CAP score (steatosis/fatty liver)
 - If elastography <8kPa, lifestyle and diet advice, refer back to GP for CV risk management.
 - If elastography >8kPa, refer to hepatology clinic.
5. Deranged lipid profile
 - The results will be communicated to the GP for full assessment (complete cardiovascular assessment, including renal and thyroid function tests) and offer starting or escalating lipid lowering therapy.
6. Deranged liver function tests
 - These will be interpreted by the clinical team leading the study in context of the medical history and other demographic and laboratory data collected ([name], [name], [name], [name]).
 - There will be provisions made to repeat the tests and send further liver screens in clinic if necessary, liaising with relevant local primary or secondary care services
7. Cirrhosis
 - Regardless of aetiology, they will be referred to a hepatology clinic.
 - The participant will be informed of the result and the referral, and the GP will be notified.

Participant withdrawal

Participants who engage with clinical testing will be linked to services and provided with support and encouragement to pursue follow up as per usual clinical pathways.

For those who provide consent for research, they will be informed that they can withdraw from the research component of the study at any time, and this will not affect the standard of care they receive. If the participant chooses to withdraw from the study, they will have two options:

1. Withdraw from the study and not be approached for further information. However, the samples and data already obtained, including audio recordings from focus groups may still be retained and used.
2. Participant requests no further contact and for their samples and data to be destroyed. Data and samples will be destroyed if they have not already been used / published as part of an analysis.

End of study

This study will run for three years, which will provide us with time to undertake community events and screening, and to follow up with relevant laboratory studies, and a period of analysis and writing up reports.

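### The hypertension follow-up rule writes its upper blood pressure level as >180/120 for the repeat and >120/180 for the advice step: most likely a transposition, to be reconciled (minor)

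*Protocol*

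**What the plan says.** The rule is in the Protocol, section 5 (Study schedule), Follow up, item 2 (Hypertension). It opens with a general statement: "We will follow NICE guidelines on hypertension diagnosis and management". Two action levels follow.

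- Lower level: "If >140/90, repeat blood pressure and take the lowest of 2 recordings". The participant is then pointed towards ambulatory monitoring, or towards a review of medication if hypertension is already diagnosed.
- Upper level, first step: "If >180/120, the blood pressure will be repeated".
- Upper level, second step: "If it remains >120/180 for 3 readings", the participant is advised to go to Accident & Emergency.

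The two steps of the upper level are consecutive sentences of one bullet. The available text states this level nowhere else (figures are not shown). Hypertension also appears in section 3.1, among the metabolic risk factors to be estimated: "Estimate the prevalence MASLD and presence of metabolic risk factors (obesity, hypertension, diabetes and dyslipidaemia". No upper blood pressure level is attached to that objective.

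**The concern.** One rule gives its level in two forms, and the second form decides whether a participant is advised to go to Accident & Emergency. This is an operative instruction for staff at community events outside a hospital. Section 16.3 (Incidental findings) relies on the same Follow up text as the plan for handling test results. Because the level is not restated elsewhere in the text, staff have no second statement in the protocol against which to check it.

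What is at stake is whether the repeat step and the advice step apply to the same participants. No estimate is at stake.

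**Working it through.** No sample size, power or precision figure depends on this point, so there is no figure of the plan to reproduce. The check compares the expressions.

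**Inputs** (all from section 5, Follow up, item 2)

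| Step | Level as written |
|---|---|
| Lower level: repeat | >140/90 |
| Upper level: repeat | >180/120 |
| Upper level: advice to attend | >120/180 on 3 readings |

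Write a reading as S/D, with S (systolic) greater than D (diastolic). The lower level and the first upper expression both put the larger number first, so a literal reader takes the order as S/D throughout. The protocol does not say whether both numbers must be exceeded or whether either is enough, so both cases are needed.

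**Case 1: both numbers must be exceeded**

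- Repeat: S > 180 and D > 120.
- Advice: S > 120 and D > 180.
- Since S > D, D > 180 already forces S > 180. The advice condition therefore reduces to D > 180 and is strictly narrower than the repeat condition.
- Example 200/130: 200 > 180 and 130 > 120, so the repeat condition is met. 200 > 120, but 130 is not above 180, so the advice condition fails. Three such readings never trigger the advice.

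**Case 2: either number suffices**

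- Repeat: S > 180 or D > 120.
- Advice: S > 120 or D > 180.
- D > 180 implies S > 180 and hence S > 120, so the advice condition reduces to S > 120.
- Every reading that meets the repeat condition also meets this one: S > 180 gives S > 120, and D > 120 gives S > D > 120. Nobody is missed, but the condition is far broader.
- Example: a reading of 140/90 has 140 > 120 and so counts towards the advice condition. It is not above 180/120, nor even above the lower level of 140/90.

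**Case 3: the second expression is the first with its numbers swapped in writing**

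- Both expressions then describe one level, and the two steps select on the same condition.

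**Result.** Read literally, the second expression matches the first in neither Case 1 nor Case 2. They agree only in Case 3, which requires the reader to correct the text.

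**The case against.** The strongest reply is that this is a slip nobody would act on. The second sentence speaks of the pressure remaining at a level, which can only mean the level in the sentence before. The two numbers are identical, and the neighbouring rule shows the order in use. The events are staffed by nurses and doctors from an experienced outreach team (section 4.3), and the item is placed under a named external guideline. All of this stands, and it makes transposition by far the likeliest explanation. It does not make the text consistent.

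A reader might infer more than the document supports, in four ways.

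- **That the protocol sets two competing rules, or a level that cannot be applied.** The backward reference and the shared numbers point to one level written in two orders.
- **That participants would miss an emergency referral.** The protocol gives advice to attend, not a referral. A participant can fail the advice condition while meeting the repeat condition only in Case 1. Even then, anyone above 180/120 is also above 140/90 (180 > 140 and 120 > 90), so the lower-level step still applies. Participants are also told their result on the day and take it away on paper.
- **That the hypertension estimate is affected.** The upper level is not attached to the objective in section 3.1, and it is not used in the sample size, eligibility or analysis sections.
- **That participant documents repeat the slip.** Section 24.1 lists a results-and-advice document and a GP letter template, but their content is not shown. Nothing indicates that either states the level.

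**Conclusion.** The point holds as a minor correction. The upper blood pressure level is written in two orders within one rule, and the second form, taken literally, does not match the first. Depending on whether both numbers or either number must be exceeded, it is narrower or far broader than the repeat condition.

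The literal mismatch rests on two assumptions: that the order of the numbers is the same in all three expressions, and that systolic exceeds diastolic. The protocol leaves open whether both numbers must be exceeded, and the direction of the mismatch depends on that. The number of participants involved cannot be derived, because the protocol gives no expected distribution of blood pressure. Sample size, precision and prevalence estimates do not change. No view is taken here on which level is clinically appropriate.

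**What to change.** Reconcile the two sentences in section 5, Follow up, item 2, so that the same pair of values in the same order is used for the repeat step and for the advice step. The clinical team should confirm the intended values. At the same time, check that any participant-facing sheet or GP letter that states the level agrees with the corrected text.

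The cost is a one-line text correction and a short document check. No design, sample size or analysis change follows.
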